#### 7. STATISTICAL ANALYSES

#### 7.1 Sample size and power considerations

Previous data showed that nt-proBNP levels decrease by about 50% within 6 months after acute myocardial infarction. To detect a relative 40% larger reduction in nt-proBNP levels in the Empagliflozin group as compared to the placebo group with a power of 80% and an alpha-level of 0.05%, and assuming a correlation for nt-proBNP levels of 0.85, a sample size of 216 subjects in each group is necessary. To account for a dropout rate of about 10% each group will consist of 238 patients.

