#### 7.2 Data analysis

Patient characteristics will be summarized. Summaries of continuous variables will be presented as means and standard deviations, if normally distributed, and as medians and inter-quartile ranges for skewed data, whilst categorical variables will be presented as frequencies and percentages. The analysis will be performed according to the intention to treat principle. All statistical tests will be two-tailed with a 5% significance level.

Analysis will be based on the intention to treat cohort, while a sensitivity analysis for the per-protocol group will be done in addition. A detailed statistical analysis plan including pre-specified subgroup analyses will be finalized ahead of database lock.

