# Application to our project

According to a similar study [2] that reported the quartiles of NT-proBNP at baseline and at 6 months follow-up and using the approximations in (2.11) and (2.12), the estimates of the parameters needed for the sample size calculation are as follows:

$$\theta_0 \approx \frac{201 + 518 + 1242}{3} = 653.66$$

$$\theta_1 \approx \frac{113 + 232 + 503}{3} = 282.66$$

$$\sigma_{0x} = \frac{1242 - 201}{2\Phi^{-1}(\frac{0.75.877 - 0.125}{877 + 0.25})} = 772.98$$

$$\sigma_{1x} \ = \ \frac{503 - 113}{2\Phi^{-1}(\frac{0.75.856 - 0.125}{856 + 0.25})} = 289.60$$

$$m_x = \frac{\sigma_{1x}^2}{\sigma_{0x}^2} = 0.14$$

Assuming  $\alpha = 5\%$  and a power  $1 - \beta = 80\%$ , the required sample size as a function of the correlation between baseline and follow-up measurements is given in tables 1, 2 and 3 according to different levels of the desired relative reduction RR = 0.3, 0.35 and 0.4.

Protocol No: Version 2.17 Date: 17 October 2022

Table 1: Sample size as a function of the correlation between baseline and follow-up measurements using a relative reduction RR=0.3

res	Correlation coefficient	Sample size in each arm	Total sample size
1	0.00	865	1730
2	0.05	837	1674
3	0.10	808	1616
	0.15	780	1560
5	0.20	751	1502
6	0.25	723	1446
4 5 6 7 8	0.30	695	1390
8	0.35	666	1332
9	0.40	638	1276
10	0.45	610	1220
11	0.50	581	1162
12	0.55	553	1106
13	0.60	524	1048
14	0.65	496	992
15	0.70	468	936
16	0.75	439	878
17	0.80	411	822
18	0.85	383	766
19	0.90	354	708
20	0.95	326	652
21	1.00	298	596

Table 2: Sample size as a function of the correlation between baseline and follow-up measurements using a relative reduction RR=0.35

res	Correlation coefficient	Sample size in each arm	Total sample size
1	0.00	636	1272
2	0.05	615	1230
	0.10	594	1188
4	0.15	573	1146
5	0.20	552	1104
6	0.25	532	1064
7	0.30	511	1022
8	0.35	490	980
9	0.40	469	938
10	0.45	448	896
11	0.50	427	854
12	0.55	407	814
13	0.60	386	772
14	0.65	365	730
15	0.70	344	688
16	0.75	323	646
17	0.80	302	604
18	0.85	282	564
19	0.90	261	522
20	0.95	240	480
21	1.00	219	438

Protocol No: Version 2.17 Date: 17 October 2022

Table 3: Sample size as a function of the correlation between baseline and follow-up measurements using a relative reduction RR = 0.4

res	Correlation coefficient	Sample size in each arm	Total sample size
1	0.00	487	974
2	0.05	471	942
3	0.10	455	910
4	0.15	439	878
5	0.20	423	846
6	0.25	407	814
7	0.30	391	782
8	0.35	375	750
9	0.40	359	718
10	0.45	344	688
11	0.50	328	656
12	0.55	312	624

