13	0.60	296	592
14	0.65	280	560
15	0.70	264	528
16	0.75	248	496
17	0.80	232	464
18	0.85	216	432
19	0.90	200	400
20	0.95	184	368
21	1.00	168	336

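### The 238 per group said to allow for about 10% dropout leaves 214, not the required 216, after a 10% loss; it covers about 9%, and the effect on power is minor

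*Protocol*

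**What the plan says.** Protocol 7.1 sets the target effect: "To detect a relative 40% larger reduction in nt-proBNP levels in the Empagliflozin group as compared to the placebo group". With 80% power and an assumed correlation of 0.85 it arrives at 216 per group. That figure comes from Appendix A, Table 3, whose row reads "18 0.85 216 432".

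Protocol 7.1 then makes the dropout adjustment in one sentence: "To account for a dropout rate of about 10% each group will consist of 238 patients". SAP 4 carries the same sentence. The resulting total of 476 appears in the protocol synopsis and in section 3.1.

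Neither document prints the inflation formula. Appendix A stops at 216 per arm and has no dropout step, so nothing elsewhere supplies or corrects the calculation.

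**The concern.** A dropout allowance should ensure that, after the expected loss, the required number remains. The loss is taken from the number enrolled, so the required number is divided by one minus the dropout rate. The printed 238 is what results from multiplying by one plus the rate instead, and that always falls a little short.

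At stake is the consistency of the paragraph that justifies the enrolment target. It calls 216 per group necessary and names a dropout rate of about 10%. At 10% its own target leaves fewer than 216.

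**Working it through.** **Inputs**

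- Means, from quartiles (Appendix A, Application to our project): baseline (201 + 518 + 1242)/3 = 653.67; 6 months (113 + 232 + 503)/3 = 282.67.
- SDs (same place): baseline 772.98; 6 months 289.60. The ratio of SDs is 0.3747 and the ratio of variances m is 0.1404.
- Correlation r = 0.85 and relative reduction 0.40 (Protocol 7.1).
- Allocation 1:1 (Appendix A, 2.1); power 80%.
- Two-sided alpha of 5%, from Appendix A and Protocol 7.2 ("All statistical tests will be two-tailed with a 5% significance level"). Protocol 7.1 and SAP 4 print 0.05%, but only 5% reproduces 216; a true 0.05% would need about 511 per arm. That misprint is a separate matter.

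**Step 1: reproduce 216**

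- Delta = 0.40 × (653.67 − 282.67) = 148.4.
- SD of change = 772.98 × √(1 + 0.1404 − 2 × 0.85 × 0.3747) = 548.46.
- Formula 2.9 (normal approximation): n = 2 × (1.960 + 0.842)² × 548.46² / 148.4² = 214.4, rounded up to 215.
- Exact two-sample t-test power: 79.93% at 215 and 80.11% at 216.

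So 216 is the smallest number per arm that reaches 80% with the t-test, and the Table 3 row is correct.

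**Step 2: reproduce 238**

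- 216 × 1.10 = 237.6, rounded up to 238. This matches exactly.
- 216 / (1 − 0.10) = 240 per arm, 480 in total. This is 2 per arm and 4 in total above the stated figures.

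**Step 3: what 238 leaves**

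- At 10% loss: 238 × 0.90 = 214.2, which is 1.8 below 216.
- Largest loss that still leaves 216: (238 − 216) / 238 = 22 / 238 = 9.24%.

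**Step 4: effect on power, same inputs**

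| Analysed per arm | t-test | Normal approximation |
|---|---|---|
| 216 | 80.1% | 80.3% |
| 214 | 79.7% | 79.9% |

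The loss is about 0.4 percentage points on either basis.

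**The case against.** Four points can be made on the other side.

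First, the multiplication is inferred. The rate is given as about 10%, and 9.2% can fairly be called that. This stands as far as the origin of 238 goes. It does not remove the shortfall: 10% is the only rate printed, and however 238 arose, it does not leave 216 after a 10% loss.

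Second, the gap is within the uncertainty of the inputs. Formula 2.9 unrounded asks for 214.4 against the 214.2 that remain. The means and SDs are approximated from quartiles, and a single step in Table 3, from a correlation of 0.85 to 0.80, moves the requirement from 216 to 232. This stands, and it is why the point is minor.

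Third, a reader might infer that 476 patients fail to deliver the claimed power, or that the trial is underpowered. The documents do not support that. The 79.7% belongs to an unadjusted t-test on change among completers. SAP 7.1 plans a mixed model on the ITT population, adjusted for baseline NT-proBNP. Patients with a week 6 or week 12 value but no week 26 value still contribute under the missing-at-random assumption, so 214 is not the size of the primary analysis set. On Appendix A's own figures, baseline adjustment would also cut the residual SD to 289.60 × √(1 − 0.85²) ≈ 153, far below the 548 used for planning. Those figures may be optimistic, and SAP 5.3.1 allows a log transformation, but 2 patients per arm would not matter to that analysis.

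Fourth, recruitment is over. The synopsis gives last patient in as December 2021, and this protocol version is dated October 2022. Only the wording can change.

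**Conclusion.** The point holds as a small arithmetic correction to Protocol 7.1 and SAP 4. The stated 238 per group covers a dropout of up to 9.2%; covering 10% takes 240. The shortfall at 10% is 2 patients per arm, worth about 0.4 points of power on the Appendix A calculation.

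This rests on reading the allowance as a loss from those enrolled, on taking the printed 10% at face value, and on 216 as the required number analysed per arm. That 238 came from multiplying by 1.10 is likely but not documented, and the conclusion does not depend on it. It does not show that the planned primary analysis lacks power.

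**What to change.** Restate the dropout sentence in Protocol 7.1 and SAP 4, for example:

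> 238 per group allows for a dropout of about 9%; at 10% dropout 214 per group remain, with power 79.7% on the Appendix A calculation.

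Printing the formula, required number / (1 − dropout rate), would let a reader check it. Table 3 and the enrolment figure of 476 stay as they are.

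The cost is one sentence in each document and a slightly less favourable power statement at 10% dropout. No patients are added and no analysis changes.

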### **Appendix C Echo Manual**

#### 1 Preamble

This manual is a summary of all echocardiographic images and loops that should be assessed as part of the EMMY trial echocardiography sub-study. All information given here is based upon the publications "Recommendations for Cardiac Chamber Quantification by Echocardiography in Adults: An Update from the American Society of Echocardiography and the European Association of Cardiovascular Imaging", published by Lang et al in 2015 and "Recommendations for the Evaluation of Left Ventricular Diastolic Function by Echocardiography: An Update from the American Society of Echocardiography and the European Association of Cardiovascular Imaging", published by Nagueh et al in 2016.

### 1.1 Equipment

All study centres will use their own equipment. The echo machines should be maintained adequately and of best available quality. The framing rate should be set to the highest possible value (preferable at least > 50 fps).

### 1.3 What do we need for analysis?

Every file must include – if the quality is sufficient – loops and images of the (1-3) parasternal long axis including M-mode of the dimensions of the left ventricle and M-mode of the dimensions of the aorta/left atrium; (4, 5) parasternal short axis on the level of the papillary muscle and on the level of the apex; (6-12) apical 4-chamber view with and without colour Doppler including one image with pulsed wave Doppler at the leaflets of the opened mitral valve and tissue Doppler on the medial mitral annulus and continuous wave Doppler at the origin of a tricuspid regurgitation (gradient over tricuspid valve); (13, 14) native apical 2-chamber view; (15) native apical 3-chamber view; and (16, 17) one loop of the apical 5-chamber view with colour Doppler and one image with the continuous wave Doppler in the aortic outflow tract. ECG leads should be connected to the echocardiography machine and ecg tracings should be recorded on each loop or image.

[figure not shown]
Protocol No: Version 2.17 Date: 17 October 2022

# 2 Echocardiographic measurements

## 2.1 The parasternal long axis (1-3)

In this axis one loop is required (1). Additionally, saved images of the linear measurements of the left ventricle (2) and the aorta/left atrium (3) each measured in M-mode.

[figure not shown]

Figure 4 Example of an M-mode in the parasternal long axis (left: left ventricle; right: aorta/left atrium)

Protocol No: Version 2.17 Date: 17 October 2022

[figure not shown]

Figure 3 Example of a parasternal long axis (loop should be recorded)

[figure not shown]

Protocol No: Version 2.17 Date: 17 October 2022

## 2.2 The parasternal short axis (4, 5)

In the parasternal short axis, 2 loops should be obtained and saved: at the level of the papillary muscles (4) and at the level of the apex (5)

[figure not shown]

Figure 4 Examples of the parasternal short axis (left: level of the papillary muscles; right: level of the apex)

2.3 The apical 4-

## chamber view (6-12)

In the apical 4-chamber view one native loop is required (6). Make sure to record the left and right ventricles and the left atrium in the full length. If the left atrium can't be recorded at full length together with the left ventricle, you should record an extra loop with focus on the left atrium (7).

[figure not shown]
Figure 5 Example of an apical 4-chamber view (left: focus on the left ventricle; right: focus on the left atrium)

Protocol No: Version 2.17 Date: 17 October 2022

Record a loop with colour Doppler placed on the left atrium (8; assessment of mitral regurgitation) and a loop with colour Doppler placed on the right atrium (9; assessment of tricuspid regurgitation). After recording loop #9 (tricuspid regurgitation), place the continuous wave Doppler directly on the origin of the jet, if present (10). The measured signal can then be used to gain information about the pulmonary artery systolic pressure.

[figure not shown]

Figure 6 Left: Example of a mitral regurgitation (colour Doppler placed on the left atrium); right: Example of a tricuspid regurgitation (colour Doppler placed on the right atrium)

[figure not shown]

[figure not shown]
Figure 7 Example of a continuous wave Doppler placed on the origin of a tricuspid regurgitation, the signal can be used to gain information on pulmonary systolic pressure

[figure not shown]
To finish the recordings in the apical 4-chamber view, two more images need to be recorded: one image with the pulsed wave Doppler placed on the leaflets of the opened mitral valve (11; assessment of E and A wave) and the pulsed wave Doppler with tissue Doppler placed on the medial mitral annulus (12; assessment of é). Both, E and é are main parameters in the evaluation of the diastolic function (Nagueh et al. 2016).

[figure not shown]

Protocol No: Version 2.17 Date: 17 October 2022

## 2.4 The apical 2 chamber view (13, [14])

Like the apical 4 chamber view, left ventricle and left atrium should be recorded in full length (13). If the left atrium can't be recorded in full length together with the left ventricle, an additional loop with focus on the left atrium **should be** recorded (14; assessment of the left atrial volume with the Biplane Area-Length Method). No further loops or images are required.

[figure not shown]

Figure 9 Example of an apical 2-chamber view (left: focus on the left ventricle; right: focus on the left atrium)

2.5

## The apical 3 chamber view (15)

In the apical 3 chamber view the left ventricle at full length, left atrium and aortic root must be visible (15). No further loops or images are required.

Protocol No: Version 2.17 Date: 17 October 2022

[figure not shown]

[figure not shown]
Figure 10 Example of an apical 3-chamber view

[figure not shown]
## 2.6 The apical 5 chamber

view (16 17)

In the apical 5 chamber view, one loop with colour Doppler over the aortic valve should be recorded (16). Finally, one image with the continuous wave Doppler placed directly on the aortic valve should be recorded (17).

Figure 11 Example of an apical 5-chamber view (Left: colour Doppler placed over the aorta to gain information of an aortic regurgitation; right: continuous wave Doppler placed on the position of the aortic valve (measurement of gradients)

#### Protocol No: Version 2.17

#### Date: 17 October 2022

### 3 Summary

ECG recordings on each loop or Image

#### **PLAX**

- 1 **Loop** of the PLAX
- 2 Image with M-mode of the left ventricular dimensions
- 3 Image with M-mode of the aortic root and the left atrium

#### PSAX

- 4 **Loop** of the PSAX at the level of the papillary muscles
- 5 **Loop** of the PSAX at the level of the apex

#### Apical 4 chamber view

- 6 Native loop of the 4-chamber view with focus on the left ventricle
- 7 Native loop of the 4-chamber view with focus on the left atrium
- 8 Loop of the 4-chamber view with colour Doppler placed on the left atrium
- 9 **Loop** of the 4-chamber view with **colour Doppler** placed on the **right atrium**
- 10 Image of the tricuspid regurgitation signal (CW Doppler on origin of jet into right atrium)
- 11 Image of E and A wave (PW Doppler placed on the leaflets of the opened mitral valve)
- 12 Image of septal é (TVI and PW Doppler placed on the medial mitral annulus)

## Apical 2 chamber view

- 13 Native loop of the 2-chamber view with focus on the left ventricle
- 14 Native loop of the 2-chamber view with focus in the left atrium

#### Apical 3 chamber view

Native loop of the 3-chamber view with focus on the left ventricle (left atrium and aortic root must be visible)

# Apical 5 chamber view

- 16 Loop of the 5-chamber view with colour Doppler placed on the aortic valve/left ventricle
- 17 Image of aortic blood outflow velocity (CW Doppler placed directly on the aortic valve)

1.1 Preface

Type 2 diabetes mellitus (T2DM) is associated with an about two to three-fold increased risk of cardiovascular events as compared with subjects without diabetes. The United Kingdom Prospective Study (UKPDS) was the first to demonstrate a reduction of macrovascular and microvascular complications in subjects with T2DM by an intensified glucose lowering treatment regimen with either insulin/sulfonylurea or metformin after long term follow up. After Rosiglitazone was removed from the European market due to ongoing uncertainty about the cardiovascular safety of this drug, the Federal Drug Administration (FDA) and the European Medicine Agency (EMEA) have issued new guidelines for new antihyperglycaemic drugs to be licensed, requiring a thorough assessment of cardiovascular safety and in most cases the performance of a large cardiovascular outcome trial. Sodium-dependent glucose cotransporter 2 (SGLT-2) is mainly expressed in human kidneys and small intestinal cells. In the proximal tubule of the nephron SGLT-2 is responsible for the reabsorption of approximately 90% of the filtrated glucose. Inhibition of SGLT-2 was shown to increase renal glucose excretion and to lower plasma glucose. Subsequently, a number of SGLT-2 inhibitors were developed and are currently approved for the treatment of T2DM.

Zinman B. et al published the results of the EMPA-REG-OUTCOME trial where the cardiovascular impact of a glucose lowering regimen including Empagliflozin as compared to usual glucose control without an SGLT-2 inhibitor was investigated. The trial demonstrated an unexpected reduction in the primary composite endpoint, comprising cardiovascular death, non-fatal myocardial infarction and non-fatal stroke. The reduction was mainly driven by a 38% relative risk reduction in cardiovascular deaths; moreover they demonstrated an impressive 35% relative risk reduction in the secondary endpoint hospitalization for heart failure. Of note, the beneficial effects observed in the Empagliflozin group seem to occur very rapidly after commencing the treatment, as shown by the early separation of the Kaplan-Meier curves. However, the mechanisms responsible for this finding remain unclear. Diuretic effects with subsequent impact on hemodynamics or potential cardioprotective effects of glucagon, whose levels rise under the treatment with SGLT-2 inhibitors and the resulting rise in ketone bodies or a small increase in haematocrit have been suggested as potential mechanisms.

We hypothesize that Empagliflozin beneficially influences the increased cardiac pre- and afterload as well as reducing the increased sodium reabsorption following myocardial damage with subsequent reduced cardiac output. Whether or not Empagliflozin has direct effects on myocardial remodelling has yet to be elucidated, yet. Moreover, recent animal data suggest that in failing heart ketone bodies seems to be an increasingly important as energy source. Empagliflozin has been shown to increase levels of ketone bodies, which might has a beneficial impact on the metabolism and energy supply of the failing heart. In addition, although SGLT-2 is not expressed in human myocardium, direct, non-SGLT-2 mediated effects on the heart muscle cannot be excluded, given that the molecule is small in size.

1.2 Scope of the analyses

These analyses will assess the efficacy and safety of Empagliflozin in improving cardiac function and biomarkers of heart failure in patients with acute myocardial infarction and will be included in the clinical study report.

2 Study Objectives and Endpoints

2.1 Study Objectives

The aim of this study is to investigate the impact of Empagliflozin on cardiac function and heart failure biomarkers in patients with acute myocardial infarction.

2.1.1 Primary objectives

The primary objective is to investigate the impact of Empagliflozin on NT-proBNP (a heart failure biomarker) in patients with myocardial infarction within 6 months after randomization.

2.1.2 Secondary objectives

Secondary objectives are as follows:

- Short term changes in NT-proBNP levels
- Short term and intermediate term changes in echocardiography parameters
- Change in levels of ketone body concentrations
- Change in HbA1c levels

- Change in body weight
- Number of hospital re-admissions due to heart failure or other causes
- Duration of hospital stay
- All-cause mortality

2.1.3 Safety objectives

- All-cause mortality
- Number of serious adverse events
- Number of severe hypoglycaemic events (i.e. requiring third party assistance)
- Number of genital infections
- Number of ketoacidotic events
- Changes in liver function parameters (AST, ALT, GGT)
- Changes in renal function parameters (creatinine, eGFR)

2.2 Endpoints

2.2.1 Primary endpoint

The primary endpoint is the change in NT-proBNP levels from randomization to week 26.

2.2.2 Secondary endpoints

Secondary endpoints include the following:

- Change of NT-proBNP between treatment groups from randomization to week 6
- Change of ejection fraction (EF) between treatment groups from randomization to week 26
- Change of ejection fraction between treatment groups from randomization to week 6
- Change of left ventricular diastolic function (LVDF) from randomization to week 26
- Change of LVDF from randomization to week 6
- Change of HbA1c between treatment groups from randomization to week 26 (in subjects with known diabetes mellitus Type 2 at randomization)
- Change of body weight between treatment groups from randomization to week 6
- Change of body weight between treatment groups from randomization to week 26
- Change of blood beta-hydroxybutyrate levels between the treatment groups from randomization to week 6

- Change of blood beta-hydroxybutyrate levels between the treatment groups from randomization to week 26
- Difference in hospital re-admissions rate due to heart failure after discharge (of the myocardial infarction event leading to trial inclusion) between the treatment groups
- The difference in the number of hospital re-admissions for any cause between the treatment groups
- The difference in the duration of hospital stay between the treatment groups after randomization

3 Study Methods

